9.5 Analysis Populations

9.5.1 Immunogenicity Analysis Populations

Per-Protocol Immunogenicity (PPI) Population

The PPI population will serve as the primary population for the analysis of immune response to each HPV-types. To be included in this population, participants must:

- (1) Have received all required vaccinations of 9vHPV vaccine with the correct dose within acceptable day ranges (see Table 5).
- (2) Have provided blood samples for serology testing within 21 to 49 days post last dose.
- (3) Be seronegative to the appropriate HPV type(s) at Day 1.

(4) Have no other protocol violations that could interfere with the evaluation of participant's immune response to the study vaccine.

61

The final determination on protocol violations, which will be used for determining the PPI population, will be made prior to the database lock and will be documented in a separate memo.

Table 5 Acceptable Day Ranges for Vaccination Visits

	Protocol Specified	Day Range for Inclusion in Statistical Analysis				
Vaccination Dose	Visit Window	(Relative to Day 1 [†])				
	3-Dose [0,2,6 re	gimen]				
Dose 1	Day 1 [†]	0				
Dose 2	Month 2 ± 3 weeks	36 to 84				
Dose 3	Month 6 ± 4 weeks	148 to 218				
	2-Dose [0,6 regimen]					
Dose 1	Day 1 [†]	0				
Dose 2	Month 6 ± 4 weeks	148 to 218				
† Day 1 refers to the date wh	en vaccination dose 1 was administer	ed.				

Table 6 Acceptable Day Ranges for Collection of Serum Samples

Study Visit	Sample Type	Target Collection Day (Relative to Day 1)†	Day Range for Inclusion in Statistical Analysis (Relative to Day 1†)			
Day 1	Serum	0	-14 to 0			
Month 7	Serum	30 days post last dose	21 to 49 post last dose			
Month 18	Serum	548	366 to 730			
Month 30	Serum	913	731 to 1004			
† Day 1 refers to the date when vaccination dose 1 was administered. For Month 7, indicated target collection/day range						
is relative to date	is relative to date of injection of last dose of 9vHPV vaccine.					

All Naïve Participants with Serology (ANPS) Population

A supportive immunogenicity analysis will be carried out on the all type-specific naïve participants with serology population. To be included in this population, participants must:

- (1) Have received at least 1 vaccination.
- (2) Have provided serum samples with evaluable results.
- (3) Be seronegative to the appropriate HPV types at Day 1.

For each of the PPI and ANPS analysis populations:

- 1) To be included in the analysis population for HPV 6 or 11, participants must be seronegative to both HPV 6 and 11 at Day 1;
- 2) To be included in the analysis population for any other vaccine HPV type, participants must be seronegative at Day 1 only for the HPV type being analyzed.

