4 STUDY DESIGN

4.1 Overall Design

V503-066-02 FINAL PROTOCOL

This is a phase 3 open-label study to evaluate the immunogenicity and safety of a 9vHPV (types 6, 11, 16, 18, 31, 33, 45, 52, and 58) vaccine (V503) in Japanese boys and girls aged 9 to 15 years. This study will consist of two periods. Period I of the study is to evaluate the immunogenicity and safety/tolerability of the 9vHPV vaccine up to the time point of Month 7. Period II of the study is to evaluate the long-term immunogenicity and safety from Month 7 to Month 30. Analysis of the base phase (Period I) for the 2-dose arm in girls aged 9 to 14 years old is planned to be conducted when all girl participants have completed their Period I (Month 7 visit) or discontinued from study before that time. Analysis of the base phase (Period I) for the 2-dose and 3-dose arms in boys and extension phase (Period II) for all arms will be conducted at the end of study.

This study will enroll approximately 300 Japanese boys and girls in total, and approximately 100 participants will be allocated to each of the following three arms:

31

- 3-dose (Day 1, Month 2 and Month 6) in boys aged 9 to 15 years
- 2-dose (Day 1 and Month 6) in boys aged 9 to 14 years
- 2-dose (Day 1 and Month 6) in girls aged 9 to 14 years

Enrollment of the girl cohort will be initiated first. Enrollment of the boy cohorts will be initiated at a later time to be determined by the Sponsor.

Blood samples will be collected on Day 1 immediately before vaccination, and subsequently Month 7, Month 18 and Month 30 to evaluate HPV antibody responses.

Participants will be followed for injection-site AEs and systemic AEs from Day 1 through Day 15 following each vaccination. SAEs will be recorded regardless of causality from the time of allocation/randomization through 6 months post last dose. Vaccine-related SAEs and deaths will be collected throughout the study. New medical conditions (defined as incident medical conditions occurring outside of a Days 1 to Days 15 period following each vaccination and not considered SAEs) will be recorded for all participants at each study visit throughout the study.

Specific procedures to be performed during the study, as well as their prescribed times and associated visit windows, are outlined in the SoA in Section 1.3. Details of each procedure are provided in Section 8.

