8.2 Immunogenicity Assessments

8.2.1 Blood Sample Collection for Serum Anti-HPV Antibody Testing

Blood samples will be collected for analysis of antibodies specific for HPV 6, 11, 16, 18, 31, 33, 45, 52, and 58 titers in serum. On Day 1, blood samples will be collected prior to the first study vaccination to identify participants who have been exposed to study vaccine HPV types prior to enrollment. Serology results on Day 1 are not part of the inclusion/exclusion criteria; thus, no participant will be excluded from the study based on these results. After Day 1, serum specimens will be collected at Month 7, Month 18, and Month 30 to evaluate persistence of immune responses.

Blood sample collection, storage, and shipment instructions for serum samples will be provided in the Laboratory Manual. Blood samples will be collected for anti-HPV antibody testing per the schedule indicated in the SoA (Section 1.3).

After completion of immunogenicity testing to evaluate the study objectives, all leftover serum samples will be stored for up to 15 years. The samples may be used to conduct any additional study-related testing, biomarker testing, or to support HPV assay development/validation activities as required by regulatory agencies or the Sponsor.

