9.2 Responsibility for Analyses/In-house Blinding

The statistical analysis of the data obtained from this study will be the responsibility of the designee/Clinical Biostatistics department of the Sponsor. This trial is being conducted as an open-label study, i.e., participants, investigators, and Sponsor personnel will be aware of participant treatment assignments after each participant is enrolled and treatment is assigned.

First database lock will be executed when all girls aged 9 to 14 years old in the 2-dose arm have either completed the Month 7 visit (1 month post last dose) or discontinued from the study before that time to report on base phase analysis for this arm.

A second database lock will be executed at end-of-study to report on base phase analysis for the 2-dose and 3-dose arms in boys and on extension phase analysis for all study arms for safety and persistence of immune response.

Summaries of the primary and secondary immunogenicity endpoints will be reported in Integrated Summary of Immunogenicity reports where in addition to reporting the immunogenicity results in this study, the study results will be compared with immunogenicity results in studies of 16 to 26 year-old Japanese males and females who received 3 doses of the 9vHPV vaccine for the purpose of immunobridging efficacy in 16 to 26 year-old Japanese males and females to 9 to 15 year-old Japanese boys and girls. The results of the 2-dose arm in girls and the 2-dose and 3-dose arms in boys will be reported in two separate integrated Summary of Immunogenicity reports. The details about the analysis will be documented in a separate iSAP.

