9.9 Sample Size and Power Calculations

A total sample size of 300 participants will be enrolled. 100 participants will be enrolled in each study arm. When the discontinuation rate and exclusion from the HPV type-specific PPI population is at most 5%, at least 95 participants in each study arm will be evaluable for the analysis of immune response at 1 month post last dose (Month 7). In each arm, at least 95 participants evaluable per study arm will allow estimation of percent seroconversion that has a corresponding 95% CI with half-width of about 3 percentage points, assuming true percent seroconversion of 99%. In addition, at least 95 participants evaluable per study arm provides at least 0.99 probability to demonstrate that the point estimate of percent seroconversion exceeds 90% for all of 9 HPV types when the true percent seroconversion is 99%. At least 95 participants evaluable per study arm provides at least 0.88 probability to attain a lower limit of 95% CI of percent seroconversion equal to or more than 90% when the true percent seroconversion is at least 99%.

For the safety analysis, all participants are expected to be evaluable. If no SAE are observed among the 100 participants per study arm, this study will provide 95% confidence that the underlying percentage of participants with an SAE is <3.0% in each study arm.

The estimate and the half-width of the 95% confidence interval for the underlying percentage of participants with the adverse event given various hypothetical observed number of participants with an adverse event within the study arm are provided in Table 9. These calculations are based on the exact binomial method proposed by Clopper and Pearson (1934).

Table 9 Estimate of Incidence of Adverse Event and Half-width of 95% Confidence Interval Based on Hypothetical Number of Participants with Adverse Event among 100 Participants in the Study Arm

Hypothetical Number of Participants with Adverse Event	Estimate of Incidence	Half-width of 95% Confidence Interval†				
1	1%	2.7%				
2	2%	3.4%				
4	4%	4.4%				
8	8%	5.8%				
16	16%	7.6%				
32	32%	9.5%				
† Based on the exact binomial method (Clopper and Pearson, 1934).						

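### Should Section 9.5.1 require judgement-based per-protocol exclusions to be settled before Month 7 titres are known?

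*Combined protocol and SAP*

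**What the plan says.** Section 9.5.1 makes the PPI population primary for immunogenicity. Criteria (1) to (3) can be checked from records: complete and correct dosing within the day ranges of Table 5, a serum sample 21 to 49 days after the last dose, and seronegativity at Day 1. Criterion (4) is a judgement: "Have no other protocol violations that could interfere with the evaluation of participant's immune response to the study vaccine". The decision on violations is due before lock and goes into a memo ("for determining the PPI population, will be made prior to the database lock and will be documented in a separate memo").

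The same section defines a supportive population, ANPS, which has no criterion (4). Its first requirement is "Have received at least 1 vaccination".

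Section 9.2 places the first lock after all girls have completed Month 7 or discontinued. For the boys, "A second database lock will be executed at end-of-study to report on base phase analysis", which agrees with Section 4.1. Section 9.2 states that the study is open-label and that assignments are known; it does not mention access to serology. Section 8.2.1 refers to a Laboratory Manual for sample handling, and Section 10.1.7 says data management procedures are provided separately. Section 9.2 leaves the cross-study bridging analysis to another document: "The details about the analysis will be documented in a separate iSAP".

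**The concern.** A deadline of database lock is not a deadline of before the results. If the boys' Month 7 sera are assayed and reported soon after collection, the staff deciding criterion (4) could know who failed to seroconvert or had a low titre. Section 9.5.1 does not list which violations count. Section 6.5, for example, asks only that certain medications and non-study vaccines be avoided where possible, so whether their use leads to exclusion is open to argument. Open-label treatment does not answer the point, because knowing the arm is different from knowing the titre.

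At stake is upward bias in the primary seroconversion estimates and in the GMTs. Section 4.2 says the GMTs will feed a cross-study comparison used to infer efficacy.

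**Working it through.** **The plan's own figures.** Section 9.9 assumes 95 evaluable participants per arm and 99% true seroconversion. With exact (Clopper-Pearson) limits, 94/95 gives 98.95% (94.27% to 99.97%), a half-width of 2.85 points, matching the stated value of about 3. A lower limit of at least 90% needs at least 92/95. The probability of that for one type is 0.984, which satisfies the stated minimum of 0.88. For nine types taken as independent it is 0.984^9 = 0.869 (computed from the unrounded value). These figures are not in dispute.

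**Length of the window.** Month 7 to Month 30 is nominally 23 months. At the extremes of the Schedule of Activities windows, with 30-day months, the latest Month 7 visit is day 180 + 28 + 49 = 257 and the earliest Month 30 visit is day 900 − 28 = 872. The gap is 872 − 257 = 615 days, or 20.5 months. When assays are run and results released is not stated, so this is a possible exposure, not a demonstrated one.

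**How often the opportunity arises.** Assume a share v of 1% to 5% of participants has an arguable criterion (4) violation, independent of response. The upper value is the whole Section 9.9 allowance for discontinuation and all type-specific PPI exclusions together, so it is generous.

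- Chance of at least one non-seroconverter with such a violation among 95, per type: 1 − (1 − 0.01v)^95 = 0.9% (v = 1%) to 4.6% (v = 5%).
- Expected number of such participants: 95 × 0.01 × v = 0.0095 to 0.0475.

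**Size when it arises.** Dropping the one non-seroconverter turns 94/95 = 98.95% into 94/94 = 100%, a rise of 1.053 points. The lower limit moves from 94.3% to 96.2%. The expected shift is 0.0095 × 1.053 = 0.010 to 0.0475 × 1.053 = 0.050 points per type. This is a ceiling under these inputs: it supposes that every arguable case among non-seroconverters is excluded and would otherwise have been kept.

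**GMT.** Removing one of 95 participants whose titre is k-fold below the arm GMT multiplies the GMT by k^(1/94). With k assumed to be 10 to 100, that is 1.025 to 1.050.

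**What ANPS can show.** Section 8.9.3 says serum is not collected at Month 7 or later from participants who did not complete the regimen, and Section 8.1.10 has a similar rule for withdrawals. ANPS entry after one dose therefore adds no partly vaccinated participants at Month 7. The remaining differences between PPI and ANPS at that visit are mainly dose correctness, the dose and serum day ranges, and criterion (4). All but the last can be checked from recorded doses and dates, so a listing of exclusions by criterion identifies the criterion (4) cases.

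**The case for a change.** The strongest case for a change is this. The omission is real: no section ties the memo to the release of cLIA results or withholds them from the deciding staff. A memo makes decisions traceable but not independent of the data. A sentence in Section 9.5.1 would be cheap and would need no new data. Two figures can be added.

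- **Across nine types.** The chance that some type in an arm offers an opportunity is 1 − (1 − v(1 − 0.99^9))^95 = 7.9% (v = 1%) or 33.7% (v = 5%) if types are independent within a participant.
- **The 90% planning level.** With 91/95 the lower limit is 89.6%; dropping one non-seroconverter gives 91/94 and 91.0%.

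The omission stands. The figures carry less weight. The 33.7% spends the whole 5% allowance on criterion (4) and assumes that failure to respond to one type says nothing about the other eight; with full concordance the range falls back to 0.9% to 4.6%. It is also the chance that an opportunity exists, not that anyone uses it. For the 90% level, 91/95 exactly has probability C(95,4) × 0.01^4 × 0.99^91 = 0.0128 at the planned rate. At least one of those four must also have an arguable violation: 1 − 0.99^4 = 0.039 to 1 − 0.95^4 = 0.185. The product is about 0.05% to 0.24% per type. The 90% is a planning benchmark in Section 9.9, not a success criterion.

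The cost is not nil either. The boys' arms would need a separate violation review where no lock is planned, and laboratory transfers would have to be sequenced.

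**Conclusion.** No change to the plan is needed. The visible text does not state that criterion (4) is decided without sight of Month 7 titres. That is a missing procedural detail of a kind that the Laboratory Manual, the data management procedures or the memo itself can cover. What the plan must fix, it fixes: the population, objective criteria for most of it, predefined serostatus cutoffs (Section 8.2.2), a documented decision before lock, and a supportive analysis without the judgement criterion for both seroconversion and GMT.

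The expected effect is at most 0.01 to 0.05 percentage points per type. One excluded low responder would raise a GMT by 2.5% to 5.0%. These sizes rest on the assumed 1% to 5% of arguable violations, their independence from response, 99% true seroconversion, and an assumed 10- to 100-fold titre deficit. Section 9.3 confirms that no hypothesis is tested here. The population for the bridging comparison is not stated in these documents, so any consequence there cannot be judged from them.

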9.5.2 Safety Analysis Population

Safety analyses will be conducted in the APaT population, which consists of all participants who received at least 1 dose of 9vHPV vaccine and have provided safety data at any time during the study. Participants will be included in the study arm corresponding to the study treatment they actually received for the analysis of safety data using the APaT population (i.e., 3 doses [0,2,6 regimen] or 2 doses [0,6 regimen] of 9vHPV vaccine). For participants who received only 1 dose of 9vHPV vaccine, or a participant allocated to the 3-dose regimen arm but received 2 doses that does not correspond to the [0,6 regimen], a safety profile listing will be created separately from the safety reports that will be provided for the 3-dose [0,2,6 regimen] and 2-dose [0,6 regimen] arms.

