6.4 Study Intervention Compliance

Interruptions from the protocol-specified vaccination plan specified in Section 1.3 require consultation between the investigator and the Sponsor and written documentation of the collaborative decision on participant management.

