7 DISCONTINUATION OF STUDY INTERVENTION AND PARTICIPANT WITHDRAWAL

7.1 Discontinuation of Study Intervention

Discontinuation of study intervention does not represent withdrawal from the study.

19-SEP-2022

As certain data on clinical events beyond study intervention discontinuation may be important to the study, they must be collected through the participant's last scheduled follow-up, even if the participant has discontinued study intervention. Therefore, all participants who discontinue study intervention prior to completion of the protocol-specified vaccination regimen will still continue to participate in the study as specified in Section 1.3 and Section 8.9.3.

41

Participants may discontinue study intervention at any time for any reason or be discontinued from the study intervention at the discretion of the investigator should any untoward effect occur. In addition, a participant may be discontinued from study intervention by the investigator or the Sponsor if study intervention is inappropriate, the study plan is violated, or for administrative and/or other safety reasons. Specific details regarding procedures to be performed at study intervention discontinuation are provided in Section 8.1.10 and Section 8.9.3.

A participant must be discontinued from study intervention but continue to be monitored in the study for any of the following reasons:

- The participant or participant's legally acceptable representative requests to discontinue study intervention.
- The participant has a medical condition or personal circumstance which, in the opinion of the investigator and/or Sponsor, placed the participant at unnecessary risk from continued administration of study intervention.

For participants who are discontinued from study intervention but continue to be monitored in the study, see Section 1.3 and Section 8.9.3 for those procedures to be completed at each specified visit.

Discontinuation from study intervention is "permanent." Once a participant is discontinued from study intervention, they shall not be allowed to restart study intervention.

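### Arm safety tables are built from the regimen received, so an SAE that ends vaccination early is listed but enters no arm's incidence or confidence interval

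*Combined protocol and SAP*

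**What the plan says.** Section 9.5.2 opens with an inclusive definition of the safety (APaT) population: "all participants who received at least 1 dose of 9vHPV vaccine and have provided safety data at any time during the study". It then places participants by regimen. They are "included in the study arm corresponding to the study treatment they actually received for the analysis of safety data", and the section spells out only two possibilities: three doses on [0,2,6] or two doses on [0,6]. Two groups fit neither: anyone who received a single dose, and a participant allocated three doses who received two that do not match [0,6]. For them, "a safety profile listing will be created separately from the safety reports that will be provided for the 3-dose" and 2-dose arms.

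Section 7.1 says a participant may "be discontinued from the study intervention at the discretion of the investigator should any untoward effect occur", and "Once a participant is discontinued from study intervention, they shall not be allowed to restart study intervention". Follow-up continues after vaccination stops.

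Section 9.1 promises SAE incidence by study arm, and Table 8 marks a within-arm 95% CI for serious AEs, both within 15 days of vaccination and at any time during the study. Section 9.9 states "For the safety analysis, all participants are expected to be evaluable" and bases both its zero-SAE statement and Table 9 on 100 participants per arm.

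**The concern.** Whether a participant counts in an arm's safety rate depends on something that happens after vaccination starts, namely whether the series continues. An SAE or severe reaction can itself stop the series. A participant stopped for an SAE after dose 1 in any arm, or after the Month 2 dose in the 3-dose arm, can never complete a tabulated regimen. That participant leaves the table because of the event the table is meant to measure, and for such events the error can only be downward.

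Safety is a primary objective, and SAEs at any time during the study are a named endpoint (Section 9.4.2). The arm-level SAE rate and its interval are what readers will quote. The rule also conflicts with the at-least-one-dose definition in the same section and with the planning basis in Section 9.9. No other section supplies an incidence table by arm covering all vaccinated participants.

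**Working it through.** **Inputs**
- Arm size: 100 (Section 9.9).
- Incidence: participants with the event divided by participants with follow-up (Section 9.6.2).
- Interval: two-sided 95% Clopper-Pearson (Table 8 footnote, Section 9.9).
- Early stops: not given. I assume 1 to 5 per 100. The upper end borrows the only planning figure, in Section 9.9: "When the discontinuation rate and exclusion from the HPV type-specific PPI population is at most 5" percent. That allowance also covers per-protocol exclusions, so 5 is an extreme value.
- Event counts are illustrative. In the SAE rows, no SAE occurs among the participants who remain in the table.

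**Formulas.** For x events in n, the lower limit is the 0.025 quantile of Beta(x, n−x+1) and the upper limit is the 0.975 quantile of Beta(x+1, n−x). At x = 0 the lower limit is 0 and the upper limit is 1 − 0.025^(1/n). The one-sided 95% upper bound at x = 0 is 1 − 0.05^(1/n).

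**The plan's own figures.** For 0/100, 1 − 0.05^(1/100) = 2.95%, which agrees with the stated <3.0%. This is the one-sided bound; the two-sided upper limit is 3.62%. For Table 9, 1/100 gives 0.025 to 5.446%, half-width (5.446 − 0.025)/2 = 2.71. The six half-widths come to 2.71, 3.40, 4.41, 5.82, 7.62 and 9.53, matching 2.7, 3.4, 4.4, 5.8, 7.6 and 9.5.

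**Direction.** Take x events among 100 vaccinated, with d participants moved to the listing and s of them having the event. The table then shows (x − s)/(100 − d). This is below x/100 whenever s/d exceeds x/100. If the event itself caused every stop, s = d and the rate always falls. For events unrelated to stopping it can move either way.

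**Results**

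| Case | As planned (95% CI) | All vaccinated (95% CI) |
|---|---|---|
| 1 stop, with SAE | 0/99 = 0% (0 to 3.66%) | 1/100 = 1% (0.03 to 5.45%) |
| 2 stops, both with SAE | 0/98 = 0% (0 to 3.69%) | 2/100 = 2% (0.24 to 7.04%) |
| 5 stops, 3 with SAE | 0/95 = 0% (0 to 3.81%) | 3/100 = 3% (0.62 to 8.52%) |
| Severe reaction, 2 diverted, both had it | 3/98 = 3.06% (0.64 to 8.69%) | 5/100 = 5% (1.64 to 11.28%) |
| Severe reaction, 2 diverted, neither had it | 5/98 = 5.10% (1.68 to 11.51%) | 5/100 = 5% (1.64 to 11.28%) |
| Common AE, 5 diverted, all had it | 75/95 = 78.9% (69.4 to 86.6%) | 80/100 = 80% (70.8 to 87.3%) |
| Common AE, 5 diverted, none had it | 80/95 = 84.2% (75.3 to 90.9%) | 80/100 = 80% (70.8 to 87.3%) |

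In the first row the one-sided bound on 0/99 is 1 − 0.05^(1/99) = 2.98%. The <3.0% statement would still appear to be met although an SAE had occurred. Counted as 1/100, the one-sided bound is 4.66%.

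**The case against.** The strongest reply is that Section 9.5.2 never says outright that these participants are excluded. It says safety analyses use APaT, and Section 9.6.2 defines the incidence denominator without requiring a completed regimen. But Section 9.6.2 gives a formula and does not say who belongs to an arm. Section 9.5.2 does, and a listing made separately from the arm reports leaves these participants in neither arm.

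The primary safety objective is worded for participants who received three doses or two doses, so a regimen-received table matches it. Counting one-dose recipients in a multi-dose arm can also dilute rates of reactions after any vaccination. Both points stand as reasons to show a completed-regimen table. Neither justifies it as the only arm-level table, given the plan's own at-least-one-dose definition.

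Several limits also stand:
- Not every incomplete series is listed. A boy allocated three doses who misses Month 2 but receives [0,6] is tabulated with the 2-dose regimen. That route is closed to someone stopped after dose 1 or after Month 2.
- SAEs in participants who complete the regimen, including those after the last dose, are unaffected. Stopping for an untoward effect is discretionary, so not every SAE removes its participant.
- The events are listed, discontinuation reasons are tabulated (Section 9.6.3), and so are the numbers receiving each dose (Section 9.11).
- The study only estimates, with no test resting on these rates. The evaluability statement in Section 9.9 is a planning expectation.
- The all-vaccinated estimates of 1% and 2% lie inside the intervals the plan would report. The problem is an outcome-dependent numerator, not an interval that rules out the truth.

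**Conclusion.** The concern holds and should be fixed. As written, an SAE that ends vaccination before the regimen is complete is removed from both parts of its arm's incidence. One such event turns 1/100 into 0/99, and two turn 2/100 into 0/98. The first two rows of Table 9 are therefore cases the rule can erase from the arm table. For severe and common reactions, the illustrated rates stay within the all-vaccinated intervals, so the material case is the rare serious event.

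The size rests on assumed stop and event counts, because the documents give neither. The mechanism does not: it follows from Sections 9.5.2 and 7.1 read together.

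**What to change.** Replace the assignment rule in Section 9.5.2 with wording such as:

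> For Table 8 incidences and CIs, each APaT participant is counted in the arm allocated at Day 1, whatever the number of doses received, except that a participant documented as having been given the other arm's regimen in error is counted by regimen received; a stopped or missed dose is not such an error.

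Keep the listing of incomplete regimens. Present the completed-regimen table, which matches the objective's wording, as a supplement.

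Section 6.4 already makes interruptions "require consultation between the investigator and the Sponsor and written documentation of the collaborative decision on participant management". That record can help separate a missed dose from a wrong regimen, but it does not classify causes, so the SAP should define a regimen error itself.

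The cost is SAP wording and a few table shells. No new data are needed, because Section 7.1 already requires follow-up after vaccination stops. Serious or severe event rates may look slightly less favourable.
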